1. INTRODUCTION

Severe acute respiratory syndrome coronavirus 2 (SARS-CoV-2) is a novel RNA betacoronavirus, initially identified in patients experiencing atypical pneumonia in Wuhan City, China (Zhu, 2020) and later identified as the causative pathogen of coronavirus disease 2019 (COVID-19) (WHO, 2020).

Coronaviruses consist of an RNA genome packaged in nucleocapsid (N) protein. The resulting capsid is surrounded by an outer envelope comprised of membrane (M) protein and envelope (E) protein, which are involved in virus assembly, and spike (S) protein, which mediates entry into host cells. The S protein is essential for virus infectivity and is the main target of the humoral immune response, as demonstrated by serology analysis of recovered COVID-19 patients (Long, 2020). By mediating binding to the host receptor angiotensin-converting enzyme 2 (ACE2), the S protein facilitates membrane fusion and entry of the virus into susceptible cells (Hoffmann, 2020). The S protein is itself composed of 2 functional subunits: the S1 subunit, which contains the receptor binding domain (RBD) responsible for binding to ACE2 on host cells, and the S2 subunit, which mediates fusion of the viral and cellular membranes (Walls, 2020).

Over 200 COVID-19 vaccines are currently in preclinical or clinical development, and many of these employ mechanisms involving S protein neutralization (WHO, 2021). On 11 Dec 2020, the Food and Drug Administration (FDA) issued the first Emergency Use Authorization (EUA) for a COVID-19 vaccine (Pfizer-BioNTech COVID-19 Vaccine) in individuals ≥ 16 years old (FDA, 2020b). Similar authorizations were subsequently issued for mRNA-1273 (18 Dec 2020), a COVID-19 vaccine developed by Moderna, as well as a vaccine developed by Janssen Pharmaceuticals (27 Feb 2021), both in individuals ≥ 18 years old (Baden, 2020). On 03 Jan 2022, the EUA of the Pfizer-BioNTech vaccine was revised to include vaccination of individuals 5-11 years old who have undergone solid organ transplantation or who are diagnosed with conditions that are considered to have an equivalent level of immunocompromise (FDA, 2022). Each of these vaccines elicit robust, dose-dependent neutralizing and other polyclonal antibodies against the S protein RBD (Polack, 2020) (Sadoff, 2021) (Jackson, 2020), and in phase 3 trials have shown over 90% (Pfizer-BioNTech, Moderna) and over 60% (Janssen) efficacy in preventing symptomatic COVID-19 illness compared with placebo (Baden, 2020) (Polack, 2020) (Sadoff, 2021).

Regeneron Pharmaceuticals, Inc. (Regeneron) has developed monoclonal antibodies (mAbs) directed against the RBD of the SARS-CoV-2 S protein. Casirivimab (REGN10933) and imdevimab (REGN10987) are human, IgG1 mAbs that bind simultaneously to the RBD and block interaction with ACE2. As a co-administered combination therapy, REGN10933+REGN10987 (casirivimab+imdevimab; also referred to by the proprietary name conditionally accepted by the FDA, REGEN-COVTM) is being evaluated for the treatment and prevention of SARS-CoV-2 infection.

REGN10933+REGN10987 exhibits potent SARS-CoV-2 neutralization in pseudovirus assays using wildtype Spike (Baum, 2020), and Spike sequences found in several variants of concern (UK B.1.1.7 [alpha], South Africa B.1.351 [beta], California B.1.429 [epsilon], India B.1.617.2 [delta], and Brazil P.1 [gamma]) (REGEN-COVTM (casirivimab and imdevimab) [HCP Fact Sheet], 2022) (Weinreich, 2020). The REGN10933+REGN10987 antibodies have significantly diminished potency and are not expected to be active against the recent Omicron variant (REGEN-COVTM (casirivimab and imdevimab) [HCP Fact Sheet], 2022).

The combination therapy is being evaluated for the treatment and prevention of SARS-CoV-2 infection, and in phase 3 clinical trials was shown to be effective and well-tolerated in the treatment of outpatient and hospitalized adults with COVID-19, and in the prevention of SARS-CoV-2 infection in adults and adolescents (Horby, 2021) (O'Brien, 2021a) (O'Brien, 2021b) (Weinreich, 2021b) (see Section 3.3.1 additional information). REGN10933+REGN10987 (1200 mg IV or SC; 600 mg of each mAb) is currently authorized under EUA for the treatment of outpatients 12 years and older who are at high risk for developing severe COVID-19 (FDA, 2020a).

The Centers for Disease Control and Prevention (CDC) currently recommends deferring the receipt of a COVID-19 vaccine dose by 30 days following the use of passive antibody therapies for post-exposure prophylaxis and by 90 days following passive antibody therapies used for the treatment of COVID-19 (CDC, 2021). Currently, however, there are no published experimental data on potential pharmacodynamic interactions between anti-SARS-CoV-2 mAbs and COVID-19 vaccines to inform this recommendation. Empirical assessment of the potential immunological impact of mAb administration on COVID-19 vaccination is thus urgently needed.

This is a phase 2, randomized, open-label, parallel group study in healthy adult volunteers to assess the immunogenicity, safety, and tolerability of Moderna mRNA-1273 vaccine when administered with REGN10933+REGN10987. A central focus of the study will be to assess whether REGN10933+REGN10987 interferes with the ability of the Moderna mRNA-1273 vaccine to elicit neutralizing antibody titers against the SARS-CoV-2 S protein, and to gain a clearer mechanistic understanding of any observed alteration of vaccine-induced humoral and cellular immune responses to various S protein epitopes. The study is designed to replicate hypothetical clinical scenarios in which mAbs may be administered in conjunction with a COVID-19 vaccine, as well as simulate different time intervals between mAb and vaccine administration (using decreasing mAb dose concentrations as a proxy) to identify optimal dose timing in the event that interference with vaccine-induced immunity is observed. A detailed discussion of the rationale for the study design is provided in Section 3.2.

Additional background information on REGN10933+REGN10987 and development program can be found in the Investigator's Brochure.

2. STUDY OBJECTIVES

2.1. Primary Objectives

The primary objectives of the study are:

- To evaluate the extent of effect, if any, of REGN10933+REGN10987 administration on vaccine-induced neutralizing antibody responses to SARS-CoV-2 by Moderna mRNA-1273
- To evaluate the time interval required between REGN10933+REGN10987 administration and Moderna mRNA-1273 vaccination, to ensure no meaningful impact on vaccine-induced neutralizing antibody responses to SARS-CoV-2

2.2. Secondary Objectives

The secondary objectives of the study are:

- To quantify the alteration of antigen specificity of vaccine-induced SARS-CoV-2 antibody responses when administered with different dose regimens of REGN10933+REGN10987
- To evaluate the safety and tolerability of REGN10933+REGN10987 and Moderna mRNA-1273 vaccine when administered in close succession
- To assess the concentrations of REGN10933 and REGN10987 in serum over time in subjects who receive REGN10933+REGN10987 and Moderna mRNA-1273 vaccine
- To evaluate the immunogenicity of REGN10933 and REGN10987 over time

2.3. Exploratory Objectives

The exploratory objectives of the study are:

- To explore circulating T cell and B cell responses to SARS-CoV-2 antigens in subjects who receive both REGN10933+REGN10987 and Moderna mRNA-1273 vaccine versus those who receive the vaccine alone
- To explore the impact of REGN10933+REGN10987 as measured by the induction of vaccine-induced binding antibodies to SARS-CoV-2 receptor-binding domain (RBD) antigens post-Moderna mRNA-1273 vaccination that compete with the same epitopes recognized by REGN10933 and/or REGN10987
- To explore how REGN10933+REGN10987 alters vaccine-induced neutralizing antibody responses, induced by Moderna mRNA-1273 vaccine, against SARS-CoV-2 variants
- To characterize viral variants by sequencing SARS-CoV-2 in subjects who become infected post-baseline
- To explore the impact on vaccine responses and the mechanism of action of REGN10933+REGN10987 as measured by experimental laboratory assays and biomarkers after vaccination with Moderna mRNA-1273
- To explore biomarkers and genomic factors associated with safety and immune responses after exposure to REGN10933+REGN10987 and Moderna mRNA-1273
- To assess immune responses in subjects who receive booster vaccinations during the study

3. HYPOTHESES AND RATIONALE

3.1. Hypotheses

The clinical hypotheses of the study are that (1) REGN10933-REGN10987 does not alter the immunogenicity of Moderna mRNA-1273 vaccine and (2) REGN10933+REGN10987 and Moderna mRNA-1273, when administered in close succession, are well tolerated.

There is no statistical hypothesis in this descriptive study (Section 11.1).

3.2. Rationale

3.2.1. Rationale for Study Design

3.2.1.1. Primary Objectives: Potential Alteration of Endogenous Immune Responses

Monoclonal antibody therapies such as REGN10933+REGN10987 will continue to play an important role in COVID-19 treatment and/or prevention, even as COVID-19 vaccination becomes more widespread. There is a theoretical risk, however, that mAb treatments may alter the vaccine-induced immune responses, by binding to and thereby blocking key antigenic determinants that generate protective immunity. The primary objective of this study is thus to understand whether REGN10933+REGN10987, when administered in the setting of treatment or prevention of COVID-19, will alter the response to COVID-19 vaccines such as Moderna mRNA-1273.

To accomplish the primary study objective, REGN10933+REGN10987 will be evaluated using dose levels that have either been authorized under EUA for the treatment of COVID-19 and/or for which clinical trial data indicate efficacy in treating or preventing COVID-19 (Section 3.2.2). The study is thus designed to mirror hypothetical clinical ‘use case’ scenarios, for which the two administration modalities of REGN10933+REGN10987 may be employed in close proximity to COVID-19 vaccination or mimic waiting for vaccination for up to 6 months after a 1200 mg dose of REGEN-COV.

For the hypothetical treatment use case (ie, administration of REGN10933+REGN10987 1200 mg IV in a SARS-CoV-2-positive individual, followed by subsequent vaccination against future infection), Moderna mRNA-1273 will be administered 14 days after intravenous REGN10933+REGN10987. The use of an intervening period of time is based on public health recommendations to avoid COVID-19 vaccination during an active SARS-CoV-2 infection. The 14-day interval was selected to ensure adequate time for the distribution of REGN10933+REGN10987 from the plasma compartment into tissues.

For the hypothetical prophylaxis use case (ie, administration of REGN10933+REGN10987 1200 mg SC in a SARS-CoV-2-negative individual for short-term protection against exposure, with administration of COVID-19 vaccination for long-term protection), REGN10933+REGN10987 will be administered on the same day as Moderna mRNA-1273. Simultaneous administration of both antibody therapy and vaccination has been used as effective post-exposure prophylaxis for several pathogens, including rabies virus and hepatitis A virus (Manning, 2008) (Nelson, 2018).

In addition to the above use case scenarios, the study will evaluate endogenous immune responses over time when 1200 mg IV of REGN10933+REGN10987 is administered 6 days after the first dose of Moderna mRNA-1273 (ie, study day 7). This interval was chosen to allow adequate

production and presentation of S protein antigens following vaccination and is thus intended to represent a scenario in which the immune system is “primed” prior to treatment with REGN10933+REGN10987. This will allow for assessment of safety of REGN10933+REGN10987 administration in close temporal proximity to vaccination. In the event REGN10933+REGN10987 is found to interfere with the endogenous immune response to vaccination when given prior to or concomitantly with vaccination, this will allow assessment of whether, in the prophylaxis setting, vaccination prior to REGN10933+REGN10987 administration will allow high risk subjects to receive both long term and short term protection from vaccination and REGN10933+REGN10987 administration followed shortly thereafter.

3.2.1.2. Primary Objectives: Exploration of Time Intervals

It is anticipated that REGN10933+REGN10987 will not alter the generation of endogenous, protective immune responses to Moderna mRNA-1273 vaccination. Vaccine responses are polyclonal, and the presence of mAb therapeutics may not alter neutralizing Ab generation to all S-protein epitopes. Additionally, we anticipate that presentation of peptides for T-cell priming will not be affected by mAb therapeutics. Finally, preliminary observations from subjects with SARS-CoV-2 infection in treatment trials of REGN10933+REGN10987 have demonstrated intact IgG responses to SARS-CoV-2 antigens.

However, it is possible that mAbs could meaningfully alter immune responses to vaccination. In light of this possibility, the other primary objective of this study is to understand the optimal time interval between mAb therapeutics and COVID-19 vaccinations. As a precautionary measure, the CDC has recommended a 90-day deferral period prior to vaccination in those who have received passive antibody therapy for COVID-19 treatment. The CDC has also recommended a 30-day deferral period prior to vaccination in those who have received passive antibody therapy for post-exposure prophylaxis. These recommendations were based on the estimated half-life of such products and the anticipated period of protection against infection when receiving anti-SARS-CoV-2 monoclonal antibodies for post-exposure prophylaxis or reinfection when receiving passive antibody therapy for treatment (CDC, 2021).

In this study, several additional doses levels below 1200 mg will be administered at day 1 (Figure 1 and Table 2). Sequentially lower dose levels were chosen as a means to vary the concentration of REGN10933+REGN10987 that exists at the time of Moderna mRNA-1273 vaccination. This method is intended to simulate various time intervals that could occur between administration of REGN10933+REGN10987 at 1200 mg and vaccination with Moderna mRNA-1273. This approach – altering the dose level rather than the time interval – was selected because REGN10933+REGN10987 concentration (and not time) is the key factor impacting the likelihood of altering vaccine responses. Moreover, the approach is operationally more feasible, and (by avoiding the need to test variable and potentially lengthy time intervals) lowers the likelihood of subjects becoming exposed to SARS-CoV-2 exposure during the study, which would confound the interpretation of results. Additional information regarding the selection of dose levels in this study is provided in Section 3.2.2.

Taken together, the primary objectives in this study are intended to provide information that may guide physicians and public health agencies in making evidence-based recommendations on the usage of the Moderna mRNA-1273 COVID-19 vaccine in the setting of REGN10933+REGN10987 therapy or prevention. As COVID-19 vaccines employing S protein

neutralization as their mode of action are likely to produce comparable antibody responses and protective immunity (an assumption supported by some initial experimental data for some vaccines (Garcia-Beltran, 2021) it is anticipated that the data generated from this study can potentially be extrapolated to the general case of S-protein-based COVID-19 vaccines given in the setting of mAbs targeting the S protein RBD.

3.2.1.3. Selection and Interpretation of Primary Endpoint

Although quantitative correlates of protective immunity against SARS-CoV-2 are not yet established, the presence of serum neutralizing antibodies has been shown to correlate with protection from viral reinfection for other respiratory viruses, including influenza virus (Verschoor, 2015) and respiratory syncytial virus (Kulkarni, 2018). Neutralizing antibody titers are accepted as a general functional biomarker of the endogenous ability to block viral infection of target cells in vivo (Jackson, 2020). In the absence of clear correlates of vaccine-induced protection against COVID-19, reduced neutralization can serve as a useful benchmark to interpret any observed impact of mAb therapy on the development of an immune response to Moderna mRNA-1273 vaccine. Accordingly, the primary objective will be assessed by quantifying endogenous neutralizing antibody titers following vaccination administered with or without REGN10933+REGN10987. While the threshold of SARS-CoV-2-neutralizing antibody titers associated with meaningful clinical efficacy in treating or preventing COVID-19 are currently unknown, this study is designed with a sufficient sample size to provide a minimal detectable difference of 0.15 log (refer to Section 11.2). This precision is considered adequate to meet the aims of this phase 2 study (ie, to both quantify the magnitude of effect for the primary endpoint and to allow assessment of the safety and tolerability of the Moderna mRNA-1273 vaccine when administered with REGN10933+REGN10987).

The primary endpoint will be assessed during the vaccine response assessment period, which includes the first 56 days after the first dose of Moderna mRNA-1273 (Section 4.1 and Section 6.1.1). SARS-CoV-2-neutralizing antibodies induced by Moderna mRNA-1273 vaccine can be detected as early as 2 weeks after the first vaccine dose, with titers peaking on day 36 (35 days after the first dose and one week after the second dose of the vaccine), and remaining at peak levels at day 57 and day 119 (pseudovirus serum neutralizing infectious dose 50 [ID₅₀] titers between 256 to 1024) (Jackson, 2020) (Widge, 2021). Assessing the primary endpoints after 56 days of the first dose of vaccine will thus maximize the ability to detect the effect of mAb administration on vaccine responses (Jackson, 2020). Additional analyses of neutralizing antibody titers at approximately 6 months, 9 months, and 1 year after vaccine administration will assess long-term/memory immune response to SARS-CoV-2 following vaccination with Moderna mRNA-1273.

An open-label design was chosen for this study, as it is considered appropriate and sufficient for achieving the primary objective, as well as the other pharmacodynamic objectives, of the study.

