- Immunogenicity, as measured by anti-drug antibodies (ADA) and neutralizing antibodies (NAb) to REGN10933 and REGN10987

Procedures and Assessments Procedures and assessments will include the following:

- Nasopharyngeal (NP) swabs for SARS-CoV-2 rapid RT-PCR testing
- Blood collection for rapid serology testing and/or central serology testing
- Serum and whole blood collection for pharmacodynamic and exploratory analyses
- Blood collection for safety labs
- Pregnancy testing

Statistical Plan

Statistical Hypothesis No statistical hypothesis testing is planned in this study. Analyses of immunogenicity, safety, tolerability, and other data will be descriptive and exploratory in nature.

Justification of Sample Size This study plans to enroll up to approximately 286 subjects, in order to achieve a target enrollment of up to approximately 30 subjects per Moderna mRNA-1273 + (REGN10933 and REGN10987) arm and 46 total Moderna mRNA-1273-alone subjects. Based on the calculations provided below, this sample size is considered appropriate to meet the aims of this phase 2 study, in that it is expected to provide adequate precision in quantifying the magnitude of effect for the primary endpoint, as well as allow for an assessment of the safety and tolerability of the Moderna mRNA-1273 vaccine when administered with REGN10933+REGN10987.

The assumed log10-scale standard deviation for the study is 0.30 log. This assumption is based on phase 1 data for the Moderna mRNA-1273 vaccine, taking the weighted average (ie, adjusting for sample sizes) across all doses (25,100, and 250 µg) and age groups (18 to 55, 56 to 70, and \geq 71 years) for the neutralizing antibody titer ID₅₀ endpoint at day 57 (Anderson, 2020) (Jackson, 2020). With a log-scale standard deviation of 0.30 for the primary endpoint and a sample size of 30 and 46 subjects per arm, the half-width of the 95% within-group confidence interval (CI) [ie, the minimal detectable difference] in this study is 0.11 log and 0.09 log respectively. For between-group comparisons, the half-width of the 95% between-group CI for any two Moderna mRNA-1273 + (REGN10933 and REGN10987) arms is 0.15 log. Additionally, the half-width of the 95% between-group CI in this study for any individual Moderna mRNA-1273 + (REGN10933 and REGN10987) arm and the total Moderna mRNA-1273 alone subjects is 0.14 log.

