The analysis set that will be used for assessment of vaccine response allows for subjects to be excluded from analysis if certain confounding criteria are met (see Section 11.3.1). If 50% of subjects are excluded from analysis (ie, 15 subjects are analyzed per individual Moderna mRNA-1273 + (REGN10933 and REGN10987) arm and 23 total Moderna mRNA-1273 alone subjects are analyzed), the half-width of the 95% between-group CI for any two Moderna mRNA-1273 + (REGN10933 and REGN10987) arms is 0.22 log. Additionally, the half-width of the 95% between-group CI for any individual Moderna mRNA-1273 + (REGN10933 and REGN10987) arm and Moderna mRNA-1273 alone subjects is 0.20 log. Under this scenario, the minimal detectable difference still remains substantially smaller than the decrease in neutralization titers observed in a separate study of sera from recipients of the Moderna mRNA-1273 vaccine who were infected with South African variants (eg, B.1.351 v1, v2, and v3) (Garcia-Beltran, 2021)

Statistical Analysis

Analysis of Primary Vaccine Response Endpoint

The primary endpoint is the 50% inhibitory dilution (ID₅₀) titers of vaccine-induced neutralizing antibodies to SARS-CoV-2 pseudovirus, assessed on 56 days after the first dose of the vaccine. The 56-day time point corresponds to study day 71 for study arms 1, 2, 3, 7, 8, 6a, and 6c, and study day 57 for study arms 4, 5, 9, 6b, and 6d.

An analysis of covariance (ANCOVA) model with treatment group as a fixed effect and age as a covariate will be fit to the data as the primary analysis.

The least squares mean estimates for the endpoint will be presented for each treatment group, as well as for the differences between treatment groups. Associated 95% CIs will also be reported for each treatment group and for between-group comparisons.

Data will be originally fitted in the log scale, and final outputs will be reported in geometric means and differences of the geometric means.

Accompanying descriptive analyses will also be provided. The analyses will be conducted based on the observed data with no imputation for missing data. Values below the limit of quantification (LOQ) will be set to half of LOQ.

Analysis of Secondary Vaccine Response Endpoints

The secondary endpoints will be analyzed in a similar manner as described for the primary endpoint.

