11.2. Justification of Sample Size

This study plans to enroll up to approximately 286 subjects, in order to achieve a target enrollment of up to approximately 30 subjects per Moderna mRNA-1273 + (REGN10933 and REGN10987) arm and 46 total Moderna mRNA-1273-alone subjects. Based on the calculations provided below, this sample size is considered appropriate to meet the aims of this phase 2 study, in that it is expected to provide adequate precision in quantifying the magnitude of effect for the primary endpoint, as well as allow for an assessment of the safety and tolerability of the Moderna mRNA-1273 vaccine when administered with REGN10933+REGN10987.

The assumed \log_{10} -scale standard deviation for the study is 0.30 log. This assumption is based on phase 1 data for the Moderna mRNA-1273 vaccine, taking the weighted average (ie, adjusting for sample sizes) across all doses (25,100, and 250 μ g) and age groups (18 to 55, 56 to 70, and \geq 71 years) for the neutralizing antibody titer ID₅₀ endpoint at day 57 (Anderson, 2020) (Jackson, 2020). With a log-scale standard deviation of 0.30 for the primary endpoint and a sample size of 30 and 46 subjects per arm (in combined study drug/vaccine and vaccine-only arms, respectively), the half-width of the 95% within-group confidence interval (CI) [ie, the minimal detectable difference] in this study is 0.11 log and 0.09 log, respectively. For between-group comparisons, the half-width of the 95% between-group CI for any two Moderna mRNA-1273 + (REGN10933 and REGN10987) arms is 0.15 log. Additionally, the half-width of the 95% between-group CI in this study for any individual Moderna mRNA-1273 + (REGN10933 and REGN10987) arm and the total Moderna mRNA-1273 alone subjects is 0.14 log.

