The analysis set that will be used for assessment of vaccine response allows for subjects to be excluded from analysis if certain confounding criteria are met (see Section 11.3.1). If 50% of subjects are excluded from analysis (ie, 15 subjects are analyzed per individual Moderna mRNA-1273 + (REGN10933 and REGN10987) arm and 23 total Moderna mRNA-1273 alone subjects are analyzed), the half-width of the 95% between group CI for any two Moderna mRNA-1273 + (REGN10933 and REGN10987) arms is 0.22 log. Additionally, the half-width of the 95% between group CI for any individual Moderna mRNA-1273 + (REGN10933 and REGN10987) arm and Moderna mRNA-1273 alone subjects is 0.20 log. Under this scenario, the minimal detectable difference still remains substantially smaller than the decrease in neutralization titers observed in a separate study of sera from recipients of the Moderna mRNA-1273 vaccine who were infected with South African variants (eg, B.1.351 v1, v2, and v3) (Garcia-Beltran, 2021)

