2.2. Sample Size and Power Considerations

This study planned to enroll up to approximately 286 subjects, in order to achieve a target enrollment of up to approximately 30 subjects per Moderna mRNA-1273 + (REGN10933 and REGN10987) arm (resulting in 46 total Moderna mRNA-1273-alone subjects).

The pooled standard deviation for the primary vaccine response endpoint of neutralizing antibody titer ID₅₀ assessed 56 days after vaccination with Moderna mRNA 1273 (pooling across doses and age groups) is 0.30 (Anderson, 2020) (Jackson, 2020). With a sample size of 30 and 46 subjects per arm in combined study drug/vaccine and pooled vaccine-only arms, respectively, the half-widths of the 95% within-group confidence interval (CI) [ie, the minimal detectable difference] in this study are 0.11 and 0.09, respectively. For between-group comparisons, the half-width of the 95% between-group CI for any two Moderna mRNA-1273 + (REGN10933 and REGN10987) arms is 0.15. Additionally, the half-width of the 95% between-group CI in this study for any individual Moderna mRNA-1273 + (REGN10933 and REGN10987) arm and the total Moderna mRNA-1273 alone subjects is 0.14.

If 50% of subjects are excluded from the Per Protocol Analysis Set (ie, 15 subjects are analyzed per individual Moderna mRNA-1273 + (REGN10933 and REGN10987) arm and 23 total Moderna mRNA-1273 alone subjects are analyzed), the half-width of the 95% between group CI for any two Moderna mRNA-1273 + (REGN10933 and REGN10987) arms is 0.22. Additionally, the half-width of the 95% between group CI for any individual Moderna mRNA-1273 + (REGN10933 and REGN10987) arm and Moderna mRNA-1273 alone subjects is 0.20. Note that it is not expected that 50% of subjects will be excluded from the Per Protocol Set (PPS); this precision statement is intended to be conservative.

Note that the mean decrease in neutralization titers in sera from recipients of the Moderna mRNA-1273 vaccine who were infected with South African variants (eg, B.1.351 v1, v2, and v3) was 1.44 in log₁₀ scale (Garcia-Beltran, 2021). While this difference is not known to be clinically relevant, it provides a useful benchmark for results of this study. The vaccine still provided similar levels of protection against severe outcomes for infection with this variant (Chamaitelly, 2021).

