5.7.1. Analysis of Primary Vaccine Response Variable

The primary endpoint is the 50% inhibitory dilution (ID_{50}) neutralizing antibody titers of vaccine-induced neutralizing antibodies to SARS-CoV-2, assessed on 56 days after the first dose of the vaccine. The 56-day time point corresponds to study day 71 for study arms 1, 2, 3, 7, 8, 6a, and 6c, and study day 57 for study arms 4, 5, 9, 6b, and 6d. For all analyses, the vaccine alone arms (i.e. arms 6a, 6b, 6c and 6d) will be pooled in the analysis.

An analysis of covariance (ANCOVA) model with treatment group as a fixed effect and age as a continuous covariate will be run in order to perform the primary analysis for the PPS. The least squares mean estimates and associated 95% confidence interval for the endpoint will be reported for each treatment group, as well as for the relative differences between each combination of Moderna mRNA-1273 vaccine and REGN10933+REGN10987 arm (i.e. arms 1 - 5, and 7 - 9) and the pooled vaccine alone group.

Data may be fitted in the log 2 scale, and final outputs of geometric means and relative differences of the geometric mean ratio will be reported through the back-transformation.

Let $\hat{\mu}_A$, $\hat{\mu}_B$ denote the least squares mean estimates and $\hat{\sigma}_A^2$, $\hat{\sigma}_B^2$, $\hat{\sigma}_{AB}$ denote the associated estimated variances and covariance for the endpoint of interest of treatment groups A and B, respectively.

Geometric means and associated 95% confidence intervals for treatment groups A and B will be calculated as:

$$2^{\hat{\mu}_A}, (2^{\hat{\mu}_A - t_{df,\alpha} \times \hat{\sigma}_A}, 2^{\hat{\mu}_A + t_{df,\alpha} \times \hat{\sigma}_A}),$$

and

$$2^{\hat{\mu}_B}, (2^{\hat{\mu}_B - t_{df,\alpha} \times \hat{\sigma}_B}, 2^{\hat{\mu}_B + t_{df,\alpha} \times \hat{\sigma}_B}).$$

Relative difference of the geometric mean ratio and associated 95% confidence interval for treatment groups A and B will be calculated as:

$$(2^{\widehat{\mu}_A - \widehat{\mu}_B} - 1) \times 100\%, \left(2^{\frac{(\widehat{\mu}_A - \widehat{\mu}_B) - t_{df, \alpha} \times \sqrt{\widehat{\sigma}_A^2 - 2\widehat{\sigma}_{AB} + \widehat{\sigma}_B^2}}{2} - 1} \right) \times 100\%, \left(2^{\frac{(\widehat{\mu}_A - \widehat{\mu}_B) + t_{df, \alpha} \times \sqrt{\widehat{\sigma}_A^2 - 2\widehat{\sigma}_{AB} + \widehat{\sigma}_B^2}}{2} - 1} \right) \times 100\%.$$

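### The 0.15 log that Protocol 3.2.1.3 calls a detectable difference is a 95% CI half-width between two antibody arms, with no power attached

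*Protocol*

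**What the plan says.** In explaining the primary endpoint, Protocol 3.2.1.3 concedes that no clinically meaningful titer threshold is known. It then offers this as the design's sensitivity: "this study is designed with a sufficient sample size to provide a minimal detectable difference of 0.15 log". It refers to Section 11.2 and, in the next sentence, calls the figure precision.

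In Protocol 11.2 the 0.15 appears once, in a sentence stating that "the half-width of the 95% between-group CI for any two Moderna mRNA-1273 + (REGN10933 and REGN10987) arms is 0.15 log". For an antibody arm against all vaccine-alone subjects the same section gives 0.14.

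The label itself is used in two further ways:

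- For within-group intervals, Protocol 11.2 writes "the half-width of the 95% within-group confidence interval (CI) [ie, the minimal detectable difference] in this study" and gives 0.11 and 0.09. The synopsis does the same, and SAP 2.2 has "95% within-group confidence interval (CI) [ie, the minimal detectable difference] in this study are 0.11 and 0.09, respectively".
- For the 50%-exclusion scenario (half-widths 0.22 and 0.20), Protocol 11.2 says "Under this scenario, the minimal detectable difference still remains substantially smaller than the decrease in neutralization titers observed in a separate study". The synopsis carries the same sentence.

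SAP 5.7.1 defines the primary contrasts as each combination arm ("i.e. arms 1 - 5, and 7 - 9) and the pooled vaccine alone group"). Protocol 11.1 plans no hypothesis test, and neither document gives a power or a type II error.

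**The concern.** A detectable difference normally means a true effect that the study would find with a stated, high probability. A CI half-width has no such probability attached. A true effect equal to the half-width gives an interval excluding zero only about half the time.

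Section 3.2.1.3 names neither the half-width nor the contrast, so its reader may take 0.15 log as a loss the study would reliably show. The figure also belongs to a comparison between two antibody arms, while the paragraph is about vaccination with or without the antibodies.

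This bears on how a result is read. The second primary objective is to find the interval that leaves no meaningful impact on the response, and Protocol 3.2.1.2 says the results may guide physicians and public health agencies. If an interval includes zero, a reader who believes 0.15 log is detectable could wrongly take a 29% loss as ruled out.

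**Working it through.** **Inputs.** SD 0.30 log10, 30 subjects per antibody arm, 46 pooled vaccine-alone, and 15 and 23 after 50% exclusion (Protocol 11.2, SAP 2.2). Intervals are 95%, taken as two-sided. The SAP 5.7.1 model has nine groups (eight antibody arms plus pooled control) and age, so residual df = 286 - 10 = 276, or 143 - 10 = 133 after 50% exclusion.

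**Step 1: reproduce the stated figures.** Half-width = t(0.975, df) × 0.30 × √(1/n1 + 1/n2), or t × 0.30/√n within a group. For 30 v 30, SE = 0.30 × √(2/30) = 0.0775. For 30 v 46, SE = 0.30 × √(1/30 + 1/46) = 0.0704.

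| Interval | Half-width, one- or two-sample df | Half-width, ANCOVA df | Stated |
|---|---|---|---|
| Within, n = 30 | 0.1120 | 0.1078 | 0.11 |
| Within, n = 46 | 0.0891 | 0.0871 | 0.09 |
| 30 v 30 | 0.1551 | 0.1525 | 0.15 |
| 30 v 46 | 0.1403 | 0.1386 | 0.14 |
| 15 v 15 | 0.2244 | 0.2167 | 0.22 |
| 15 v 23 | 0.2019 | 0.1969 | 0.20 |

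The ANCOVA-df column rounds to all six stated figures. They are half-widths, with no power term in them.

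**Step 2: chance that the CI excludes zero when the true difference is 0.15.** The normal approximation is Φ(0.15/SE - 1.96).

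- 30 v 30: 0.15/0.0775 = 1.94, giving 0.491. Noncentral t gives 0.478 (two-sample df) or 0.488 (ANCOVA df).
- 30 v 46: 0.15/0.0704 = 2.13, giving 0.568. Noncentral t gives 0.557 or 0.565.

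A simulation of the nine-group ANCOVA with age (20,000 runs) gave 0.485 and 0.558. For a true 0.14 in the primary contrast, its own stated half-width, the two-sample noncentral t gives 0.501.

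**Step 3: the difference that carries a given power.** The documents state no power, so 80% and 90% are assumptions. The normal approximation is (1.960 + z_power) × SE. At 80% this is 2.802 × 0.0704 = 0.197 for 30 v 46 and 2.802 × 0.0775 = 0.217 for 30 v 30. Noncentral t values (two-sample df / ANCOVA df):

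| Contrast | 80% power | 90% power |
|---|---|---|
| 30 v 46 | 0.200 / 0.198 | 0.231 / 0.229 |
| 30 v 30 | 0.221 / 0.218 | 0.255 / 0.252 |
| 15 v 23 | 0.287 / 0.281 | 0.332 / 0.325 |
| 15 v 15 | 0.318 / 0.309 | 0.368 / 0.358 |

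**Step 4: translate to titer loss.** Loss = 1 - 10^(-d). A d of 0.15 is a 29% loss, 0.20 is 37% and 0.22 is 40%.

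**Step 5: the benchmark.** SAP 2.2 gives 1.44 log10 for the variant comparison. The largest 80%-power figure, 0.318, is 0.318/1.44 = 22% of it, so that comparison holds under either reading.

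**The case against.** The strongest defence is that the documents define their own term. The bracket in Protocol 11.2, the synopsis and SAP 2.2 equates it with a CI half-width, 3.2.1.3 points to 11.2, and the next sentence there speaks of precision. Without a power term, the phrase can mean the smallest observed difference whose interval excludes zero, which is the half-width. The study is descriptive, so sizing it by interval width is proper and no power calculation is missing. Also, 0.15 is the less favourable of the two full-sample between-group figures, and Protocol 11.4.3 plans between-group intervals without restricting them to comparisons with control.

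Much of this stands. The sizing method suits the design, the half-widths are right, quoting 0.15 instead of 0.14 overstates nothing as precision, and Protocol 11.2 and SAP 2.2 name the between-group figures correctly.

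It does not rescue the label. The bracket is attached to within-group half-widths, which are not differences between anything, so it cannot define 0.15 as a detectable difference between arms. The smallest observed difference that excludes zero is also not a true difference the study would detect, and 3.2.1.3 presents its figure as what the sample size provides. If precision is meant, the text can say so.

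**Conclusion.** The point holds as an error of labelling. The arithmetic behind the stated figures is sound. The 0.15 log in Protocol 3.2.1.3 is the half-width between two antibody arms, not a difference the study would reliably detect and not the half-width of the primary contrast. A true loss of that size would give an interval excluding zero about 56% of the time against pooled controls and 48-49% of the time between antibody arms. At an assumed 80% power the corresponding differences are about 0.20 and 0.22 log10.

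These figures assume an SD of 0.30, full enrolment, and all 46 controls pooled across waves as SAP 5.7.1 specifies. The consequence is confined to how the precision claim is read: estimates, intervals, sample size and the benchmark comparison do not change. The wording should be corrected.

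**What to change.** Make six wording edits:

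1. Protocol 3.2.1.3: replace the detectable-difference claim with 95% between-group CI half-widths of 0.14 log (antibody arm v pooled vaccine-alone) and 0.15 log (between two antibody arms).
2. Synopsis, Protocol 11.2 and SAP 2.2: delete the bracketed gloss on the within-group half-widths (three edits).
3. Synopsis and Protocol 11.2, 50%-exclusion paragraphs: replace the detectable-difference term with CI half-width (two edits).

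If the sponsor wants to keep a detectable difference, it should state the assumed power beside it. At 80%, two-sided 5% and SD 0.30, the figures are about 0.20 log10 (30 v 46) and 0.22 (30 v 30). With 50% excluded they are 0.28-0.29 (15 v 23) and 0.31-0.32 (15 v 15).

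The cost is editorial, with no extra subjects and no change to any analysis. A detectable difference with its power stated will look less favourable than 0.14-0.15.
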